# 8.2.7 Subgroup Analyses and Effect of Baseline Factors

To assess whether the treatment effect at Week 52 is consistent across various subgroups, the estimate of the between-group treatment effect (with a nominal 95% CI) for the primary endpoint will be estimated and plotted within each category of the following classification variables:

- Baseline A1C levels: by categories: <8.0%; ≥8.0%
- Age categories:  $\leq$  or > median age
- Gender (female; male)
- Race (White, Black, Asian, Other)
- Ethnicity (Hispanic or Latino, Not Hispanic or Latino)
- BMI ( $\leq$  or > median)
- Prior antihyperglycemic therapy (monotherapy or dual therapy)
- Time since diagnosis of Diabetes ( $\leq$  or > median years)

For the subgroups that have only 2 categories, if the sample size is not at least 20 subjects in all of the treatment groups in each subgroup category, then that subgroup analysis will not be performed. For the race subgroup analysis, if the sample size is not at least 20 subjects in all of the treatment groups in a certain race category, then that race will be combined with the "Other" race category. The consistency of the treatment effect will be assessed in the context of a repeated measures ANCOVA (RMANCOVA) method, which is a generalization of the standard ANCOVA to accommodate repeated measurements. The RMANCOVA model will adjust for baseline value for A1C, treatment, baseline eGFR, subgroup, and treatment-bysubgroup interaction. Time is treated as a categorical variable and time-specific versions of each term listed above at each week will be used to acknowledge the repeated nature of the measurements. An unstructured covariance matrix will be used to model the correlation among repeated measurements. For subgroup analyses based on factors that are already in the main model, the respective term will appear in the model only once. Treatment effects and nominal 95% confidence intervals by category for the classification variables listed above will be reported as well as presented graphically. Formal statistical testing of treatment-by-subgroup interactions will not be performed.

**Protocol/Amendment No.:** 002-01

The treatment effect across trial centers will be summarized for A1C at Week 52 with descriptive statistics.

Results from the subgroup analyses should be reviewed cautiously. Because sample sizes within subgroups will be smaller than the overall trial sample size, estimation may not be precise and 95% CIs will usually be wide in the subgroup analyses.

# 8.2.8 Interim Analyses

In order to support regulatory filings and safety updates, data will be summarized after all subjects complete Phase A (Week 0 to Week 52). Investigators and subjects will remain blinded to study drug treatment assignment until all subjects have completed the trial. This is not considered as an interim analysis.

Confirmed cardiovascular events from this study will be used to perform program-wide meta-analyses to meet regulatory requirements for the assessment of CV safety. The DMC will have the option to recommend an early stop for safety. Aggregate level data on confirmed CV events from this study will be analyzed in a separate report.

# **8.2.9** Compliance (Medication Adherence)

The computation of compliance will be based on the study medication case report form. Both the assigned treatment and any matching placebo tablets or capsules will be encompassed in the compliance calculation.

For each subject, percent compliance will be calculated using the following formula:

Compliance = 
$$\frac{\text{Number of Compliant Days}}{\text{Number of Days in the Double-blind Treatment Period}} \times 100\%.$$

A day within the double-blinded treatment period will be a compliant day if a patient is compliant for both ertugliflozin/matching placebo and glimepiride/matching placebo (see the definition below); otherwise, it is a non-compliant day. If the study medication eCRF indicates general compliance problems with any blinded therapy, the subject will be considered non-compliant for that day regardless of the number of tablets or capsules reported.

The "Number of Days in Double-blind Treatment Period" is defined for each subject as the total number of days from the first dose of double-blind study medication to the last day of study medication for ertugliflozin/matching placebo or sitagliptin/matching placebo.

Summary statistics will be provided on percent compliance by treatment group.

Protocol/Amendment No.: 002-01

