**Table 4 Trial Treatments** 

Treatment Group	Drug/Dose	Use	Dose Frequency/ Treatment Period	Route of Administration		
	matching placebo for ertugliflozin 5 mg	placebo				
placebo run-in (all groups)	matching placebo for ertugliflozin 10 mg	(trial drug)	q.d. for 2 weeks	oral		
	matching placebo for glimepiride 1 mg	placebo (active-comparator)				
	ertugliflozin 5 mg	investigational (trial drug)				
	matching placebo for ertugliflozin 10 mg	placebo (trial drug)	q.d. for 104			
ertugliflozin 5 mg group	matching placebo for glimepiride 1 mg	placebo	weeks	oral		
	matching placebo for glimepiride 2 mg	(active-comparator)				
	ertugliflozin 5 mg	investigational				
	ertugliflozin 10 mg	(trial drug)				
ertugliflozin 15 mg group	matching placebo for glimepiride 1 mg	placebo	q.d. for 104 weeks	oral		
	matching placebo for glimepiride 2 mg	(active-comparator)				

**Protocol/Amendment No.:** 002-01

Treatment Group	Drug/Dose	Use	Dose Frequency/ Treatment Period	Route of Administration	
	glimepiride 1 mg	active-comparator			
	glimepiride 2 mg				
glimepiride group	matching placebo for ertugliflozin 5 mg	placebo	q.d. for 104 weeks	oral	
	matching placebo for ertugliflozin 10 mg	(trial drug)			
sitagliptin rescue medication	open-label sitagliptin according to local country label	rescue medication	q.d. as required	oral	

The first doses of single-blind matching placebo for ertugliflozin and matching placebo for glimepiride will be administered at the trial site as witnessed doses at Visit 3/Week -2 or combined Visit 2/3. The first doses of double-blind ertugliflozin/matching placebo and glimepiride/matching placebo will be administered at the trial site as witnessed doses at Visit 4/Randomization (Day 1). Subsequent dosing will be performed once-daily by the subject unsupervised at his/her home at approximately the same time each day in the morning.

Supply of background metformin will be the responsibility of the subject throughout the duration of the trial.

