# **8.2.2.1** Efficacy Analysis Populations

The FAS population will be the primary analysis population for all efficacy endpoints.

For analyses that use the cLDA model described in Section 8.2.3.1, the FAS population, defined separately for each analysis endpoint, consists of all randomized subjects who:

- receive at least one dose of study treatment;
- have a baseline measurement or a post-randomization measurement for the analysis endpoint subsequent to at least one dose of study treatment.

For secondary analyses that use the ANCOVA model with last-observation-carried-forward, the FAS population consists of all randomized subjects who took at least one dose of study treatment, and have measurements for the analysis endpoint both at baseline and at one or more post-baseline time points.

A secondary population for analyzing primary and key secondary efficacy endpoints at Week 52 and Week 104 will be the Per-Protocol (PP) population. All randomized subjects who take at least one dose of study medication, with a measurement of the analysis endpoint at both baseline and in the day range for the time point of interest (Week 52 or Week 104), without any of the following protocol deviations will be included in this population.

Protocol/Amendment No.: 002-01

• Drug compliance <75%, using the compliance definition provided in Section 8.2.9.

- Use of prohibited antihyperglycemic medications (found in Section 5.5) for a total of ≥14 days or ≥7 consecutive days after randomization and within 180 days prior to the analysis time point.
- Use of pharmacologic doses of corticosteroids for ≥2 consecutive weeks after randomization and within 180 days prior to the analysis time point
- Incorrect double-blind study medication, or a change in metformin dose, for  $\ge 14$  consecutive days during the last 180 days of the trial period of interest

Protocol deviations are not just a repetition of the exclusion and inclusion criteria in the protocol, but a clinical assessment of deviations from the protocol-specified criteria that will either affect or confound the measures of efficacy. Any patient meeting any of the above criteria during the trial period of interest (Week 0 to Week 52 or Week 0 to Week 104) will be excluded from the per-protocol population for that period.

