The final determination on protocol deviations, and thereby the composition of the PP population, will be made prior to the final unblinding of the database at Week 52 and Week 104 and will be documented in separate memos.

A modified FAS (mFAS) population, defined as all subjects in the FAS who do not have any of the protocol deviations defined above, will be an additional secondary population. Subjects who discontinue prematurely without a protocol deviation will be included in the mFAS. Analyses will be performed in this population only if its size differs from that of the PP population by more than 2% of patients in any arm.

Any substantial differences between conclusions based on the FAS, PP, and (if applicable) mFAS populations will be investigated. The number of subjects included in the FAS, PP, and mFAS populations may vary across endpoints due to the degree of missing data for each endpoint.

Data after the initiation of rescue therapy or after a subject undergoes bariatric surgery will be censored (i.e., treated as missing) from analyses of efficacy endpoints.

The time-to-rescue analysis will be performed in the All-Subjects-Treated population.

For all efficacy analyses, subjects will be counted in the treatment group to which they were randomized, regardless of the treatment received during the course of the trial. Details on the approach to handling missing data are provided in Section 8.2.3, Statistical Methods.

**Protocol/Amendment No.:** 002-01

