- Imputation of "Missing=Not at Goal". The percentages of subjects at target A1C control at Week 52 will be analyzed assuming that all missing Week 52 A1C values were not at target.
- LOCF. Endpoints analyzed via cLDA will be re-analyzed using ANCOVA using the last-observation-carried-forward approach to impute missing values.
- Additional models. Specific details for these models will be provided prior to unblinding.
  - Models that assume that the distribution of the missing data differs from the distribution of the observed data will be run. Different assumptions for the missing data distribution will be considered, including MNAR.
  - o If >5% of the subjects in any treatment group were <75% compliant with study medication (using the definition in Section 8.2.10), at least one model will account for compliance.

Further investigation will be performed if the results from these sensitivity analyses are not consistent with results from the primary analyses.

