# 9.0 LABELING, PACKAGING, STORAGE AND RETURN OF CLINICAL SUPPLIES

# 9.1 Investigational Product

The investigator shall take responsibility for and shall take all steps to maintain appropriate records and ensure appropriate supply, storage, handling, distribution and usage of investigational product in accordance with the protocol and any applicable laws and regulations.

Clinical Supplies will be provided by the Sponsor as summarized in Table 16.

Table 16 Product Descriptions

Product Name & Potency	Dosage Form	
Ertugliflozin 5 mg	Tablet	
Placebo to match Ertugliflozin 5 mg	Tablet	
Ertugliflozin 10 mg	Tablet	
Placebo to match Ertugliflozin 10 mg	Tablet	
Glimepiride 1 mg	Tablet or Capsule	
Placebo to match Glimepiride 1 mg	Tablet or Capsule	
Glimepiride 2 mg	Tablet or Capsule	
Placebo to match Glimepiride 2 mg	Tablet or Capsule	

All placebos were created by the Sponsor to match the active product.

All other supplies not indicated in Table 16 above will be provided centrally by the Sponsor or locally by the trial site, subsidiary or designee, depending on local country operational or regulatory requirements.

For any commercially available product that is provided by the trial site, subsidiary or designee every attempt will be made to source these supplies from a single lot/batch number. The trial site will be responsible for recording the lot number, manufacturer and expiry date of any locally purchased product.

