# **Directions:**

- Print the Glimepiride Dosing Instruction log.
- Clinic Visits: The investigator (or designee) should enter the date and dosing instructions for glimepiride/matching placebo (Bottle F [1 mg tablets or capsules] and Bottle G [2 mg tablets or capsules]) and provide the log to the subject.
- Telephone Contacts: The subject should enter the date and dosing instructions for glimepiride/matching placebo (Bottles F [1 mg tablets or capsules] and Bottle G [2 mg tablets or capsules]) as specified by site personnel during telephone contacts.

04T4BY

**Protocol/Amendment No.:** 002-01

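### Section 8.2.9 ends the compliance period on a blinded sitagliptin pair this trial does not have and omits glimepiride/placebo, so a subject who stops only the ertugliflozin/placebo tablets can escape the 75% rule

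*Combined protocol and SAP*

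**What the plan says.** Section 8.2.9 defines percent compliance as compliant days divided by days in the double-blind treatment period.

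- **Numerator.** A day counts only if the subject was "compliant for both ertugliflozin/matching placebo and glimepiride/matching placebo". Compliant days are then defined separately for those two drugs and for no other.
- **Denominator.** The period starts at the first double-blind dose and ends on "the last day of study medication for ertugliflozin/matching placebo or sitagliptin/matching placebo".
- **Sitagliptin's role.** Table 4 lists it only as rescue: "open-label sitagliptin according to local country label". Table 16 lists placebos for ertugliflozin and glimepiride (for example "Placebo to match Glimepiride 1 mg") and none for sitagliptin.
- **Where the result is used.** Section 8.2.2.1 excludes subjects from PP for "Drug compliance <75%, using the compliance definition provided in Section 8.2.9", and mFAS applies the same deviations. In the Missing Data part of Section 8.2.3.1, if more than 5% of any treatment group were "<75% compliant with study medication (using the definition in Section 8.2.10), at least one model will account for compliance".

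Section 8.2 states that no separate SAP will be issued, so Section 8.2.9 is the only definition. The current amendment edited that section to add capsules, and this sentence still stands.

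**The concern.** The numerator and denominator refer to different pairs of drugs. The numerator needs both blinded components. The denominator names one of them plus a pair that does not exist, and leaves out the other. The word *or* is also not defined as the earlier or the later date.

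If the non-existent pair is ignored, the period closes at the last ertugliflozin/placebo dose. Days after that on glimepiride/placebo alone are non-compliant by the numerator rule, but they fall outside the period and are never counted. The eCRF override for general compliance problems cannot correct this, because it acts only on days within the period.

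At stake are membership of two secondary populations, the compliance summaries, and whether the compliance-adjusted sensitivity model is run. The trigger for that model also cites Section 8.2.10, which is Extent of Exposure and contains no compliance definition.

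**Working it through.** **Planned figures first.** Section 8.2.6 gives 97% power (337 effective subjects per arm) and 92% (257 per arm, PP), with margin 0.3%, true difference 0%, SD 1% and two-sided alpha 0.05. Power = Φ(0.3/√(2/n) − 1.96).

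- n = 337: √(2/337) = 0.0770; 0.3/0.0770 − 1.96 = 1.93; power 97.3%; 95% CI half-width 0.151.
- n = 257: √(2/257) = 0.0882; 0.3/0.0882 − 1.96 = 1.44; power 92.5%; half-width 0.173.

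Both agree with the plan to within a percentage point. The compliance formula enters neither, so no stated sample size or power changes.

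**Compliance for illustrative subjects.** Assumptions: Phase A is 52 × 7 = 364 days, and every day is compliant until the stated stop. Let E and G be the last days of ertugliflozin/placebo and glimepiride/placebo, and C the days compliant with both. As written, the score is C/E. With the drug name corrected, it is C divided by the earlier or the later of E and G.

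| Subject | C | As written | Name corrected, earlier date | Name corrected, later date |
|---|---|---|---|---|
| E = 182 (Week 26), G = 364 | 182 | 182/182 = 100% | 182/182 = 100% | 182/364 = 50.0% |
| E = 260, G = 364 | 260 | 260/260 = 100% | 260/260 = 100% | 260/364 = 71.4% |
| G = 260, no physician-titration flag, E = 364 | 260 | 260/364 = 71.4% | 260/260 = 100% | 260/364 = 71.4% |

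**Break-even.** 0.75 × 364 = 273 days, or Week 39. A subject in the first pattern who stops ertugliflozin/placebo before Week 39 belongs below 75% but scores 100% as written.

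**The permitted case.** Section 5.2.1.2.2 lets a subject stay in the trial with glimepiride/placebo interrupted. The period then runs to the last ertugliflozin/placebo dose, both as written and with the later date. Zero-tablet days attributed to the physician's titration decision count as compliant. The score is the same either way.

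**What the table shows.** Correcting the drug name alone is not enough. With the earlier date the first two subjects still score 100%, and the third, now scored correctly, would rise from 71.4% to 100%.

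**The case against.** **It is an obvious slip.** The term being defined is the double-blind treatment period, and the two drugs meant are named just before. This stands as to intent: it is very probably a wrong drug name. It does not settle *or*, and the last column of the table depends on that.

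**The pattern is not provided for.** Section 5.2.1.3 allows no change to the ertugliflozin/placebo dose, and Section 5.8 discontinues blinded product as a whole. Only glimepiride/placebo may be interrupted on its own. Section 7.1.1.8 requires sponsor consultation for interruptions of 7 days or more. This stands, and it makes the case likely rare. It remains possible because glimepiride/placebo comes in its own bottles ("Bottle F [1 mg tablets or capsules] and Bottle G [2 mg tablets or capsules"), and a compliance rule exists to detect unplanned behaviour.

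**Blinded review would catch it.** Section 8.2.2.1 describes deviations as a clinical assessment, with PP membership settled in memos before unblinding. It also excludes incorrect double-blind medication for 14 or more consecutive days in the last 180 days, but does not say that this covers omitted tablets. These are partial safeguards. They do not repair the formula.

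**A stronger reading a reader might infer** is that open-label sitagliptin days count, so that adherent rescued subjects are wrongly dropped. For example, stopping blinded drug at Week 30 and taking sitagliptin to Week 52 would give 210/364 = 57.7% instead of 210/210 = 100%. The documents do not support giving this much weight. It contradicts the double-blind period being defined, needs *or* to mean the later date, and needs sitagliptin dosing records after blinded drug stops. Section 5.8.1 shows continued supply and telephone follow-up but no such records. Post-rescue efficacy data are censored, so rescued subjects would generally lack the Week 52 value PP requires. Any effect would fall mainly on the trigger and on mFAS, of which the plan says "Subjects who discontinue prematurely without a protocol deviation will be included in the mFAS".

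**Conclusion.** The sentence is wrong as written, and nothing else in the document corrects it. The consequence is minor. Followed literally, it can score a subject at 100% who should score 50%, and so keep that subject in PP and mFAS and out of the count for the more-than-5% trigger. This rests on the subject stopping ertugliflozin/placebo alone and continuing glimepiride/placebo. The documents give no expected number of such subjects.

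The direction depends on the arm. In an ertugliflozin arm such a subject is off active study drug, so retention would be expected to dilute the PP comparison and work against non-inferiority. In the glimepiride arm the subject is still on active comparator, and no such dilution arises.

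A reader might also infer that the primary non-inferiority result is at risk. It is not: the primary cLDA analysis in the full analysis set makes no use of compliance, and the sample size and power stand. Confidence is high for the textual error and lower for how often it would matter.

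**What to change.** Before the Week 52 unblinding, and before protocol deviators are identified:

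1. In the denominator sentence of Section 8.2.9, replace sitagliptin/matching placebo with glimepiride/matching placebo.
2. State that the period ends at the later of the two blinded components' last-dose dates. The documents do not dictate this choice, but it is the one consistent with a numerator that requires both drugs, and it leaves the permitted glimepiride/placebo interruption scored as now.
3. State that open-label sitagliptin days do not count.
4. In the Missing Data part of Section 8.2.3.1, change the compliance reference from Section 8.2.10 to Section 8.2.9.

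The cost is wording, plus a check that the derivation program uses both blinded drugs' last-dose dates. No new data, visits, subjects or eCRF fields are needed. The downside is that PP and mFAS may lose any subjects who stopped only the ertugliflozin/placebo tablets, which is what the both-drugs rule implies.

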# The definition of compliant days for glimepiride /matching placebo

The compliance will be based on the number of compliant days rather than the number of study therapy tablets or capsules taken because the dosing will vary for different subjects and/or different visits. A day within the double-blind Treatment Period will be considered a compliant day if the subject was compliant on that day with glimepiride or matching placebo, defined as follows:

• the subject took at least one tablet or capsule of glimepiride or matching placebo, or the subject took 0 tablets or capsules of glimepiride or matching placebo with an accompanying indication on the eCRF that this occurred due to the physician's decision to titrate. If only the first in a series of consecutive eCRFs with 0 tablets or capsules recorded has an indication that this occurred due to the physician's decision to titrate, all eCRFs in the series will be considered to represent compliant days.

# The definition of compliant days for ertugliflozin /matching placebo

A day within the Double-blind Treatment period will be considered a compliant day to ertugliflozin/matching placebo if the patient reports taking 1 tablet of ertugliflozin 5 mg/matching placebo and 1 tablet of ertugliflozin 10 mg/matching placebo from the correct bottle.

### 8.2.10 Extent of Exposure

The extent of exposure to double-blinded study treatment will be evaluated by summary statistics (N, mean, median, standard deviation and range) and frequencies for the "Number of Days on Therapy" by treatment group, based on daily dosing records on the study medication eCRF.

**Protocol/Amendment No.:** 002-01

